	
Alpha-Stim AID Cranial Electrotherapy Stimulations (CES) for participants with a primary working diagnosis of generalised anxiety disorder (GAD), in terms of health and social care service cost, and patient cost, from baseline to week 24, following previous treatment with low intensity psychological therapy intervention.
	
See Appendix B
 
The CSRI, adapted for use for anxiety disorders in primary care and community settings, is a measure of the full health and social care cost and patient cost of treatment.
 
The endpoint will be the cost impact from baseline to week 24.
 
EQ-5D-5L
 
See Appendix C
 
The EQ-5D-5L is a participant-reported measure of health utility and quality of life used by NICE to generate QALYs for cost effectiveness assessments. The EQ-5D-5L uses 6 items.
 
The endpoint will be the change in EQ-5D-5L for participants from baseline to week 24.
 
Work and Social Adjustment Scale (WASA)
 
See Appendix D
 
The WASA scale is a participant-reported measure of work and social function. The WASA scale uses 5 items.
 
The endpoint will be the change in WASA scale score for participants from baseline to week 24.

Tertiary
	
The tertiary objective of this study is to evaluate the clinical effectiveness of treatment with Alpha-Stim AID Cranial Electrotherapy Stimulations (CES) for depression and insomnia in participants with a
	
PHQ-9
 
See Appendix E
 
The PHQ-9 is a participant-reported measure of depressive symptomatology.

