#### 3.2 Secondary objectives

The secondary objective of this study is to evaluate the cost effectiveness of treatment with Alpha-Stim AID cranial electrotherapy stimulations (CES) for participants with a primary working diagnosis of generalised anxiety disorder (GAD), in terms of health and social care service cost, and patient cost, over the previous 12 weeks, from baseline to week 24, following previous treatment with low intensity psychological therapy intervention.

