#### 3.5 Secondary outcome measures

The secondary objective will be measured using the Client Service Receipt Inventory (CSRI), adapted for use for anxiety disorders in primary care and community settings, which is a measure of the full health and social care cost and patient cost of treatment. Additionally, the objective will be measured using the EQ-5D-5L, which is a participant-reported measure of health utility and quality of life used by NICE to generate QALYs for cost effectiveness assessments, and uses 6 items. Finally, the objective will be measured using the Work and Social Adjustment Scale (WASA) which is a participant-reported measure of work and social function, and uses 8 items.

- The outcome measure for **CSRQ** is the change in cost impact for previous 12 weeks from baseline to week 24.
- The outcome measure for **EQ-5D-5L** is the change for participants from baseline to week 24.
- The outcome measure for **WASA** is the change for participants from baseline to week 24.

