## 4 STUDY DESIGN

This is a single-centre, naturalistic post-market clinical study of one CE marked device within intended purpose over 24-week follow-up period. The study will enrol patients with a primary working diagnosis of moderate-to-severe GAD who did not improve (continued to have a primary working diagnosis of moderate-to-severe GAD) with previous low intensity psychological therapy intervention.

Participants indicated for high intensity psychological therapy intervention will be approached by their routine care provider (either a Psychological Wellbeing Practitioner (PWP) or Cognitive Behavioural Therapist) with information about this study when they are contacted to discuss a step-up to step 3 high intensity therapy. From this initial approach, the current minimum waiting time for access to such therapy interventions is at least 6 - 8 weeks.

Participants who consent to enrolment will undertake 60 minute self-directed Alpha-Stim AID CES treatment sessions in their own homes on a daily basis for 6 weeks. During this 6-week period, participants will be on the waiting list for high intensity psychological therapy intervention.

Following 6 weeks of Alpha-Stim AID device treatment, participants have the option to receive a further 6 weeks of treatment, which may coincide with start of high intensity psychological therapy interventions as clinically indicated. This option is available to make the study design more comparable to real-world scenarios.

Participants wishing to discontinue use of the Alpha-Stim AID device will return the device and any unused electrode pads to the research nurse via pre postage paid envelope.

Following a maximum of 12 weeks' treatment with Alpha-Stim AID device, all participants will cease to receive treatment on study. At this time-point, all participants will return the device and any unused electrode pads to the research nurse via pre postage paid envelope.

Participants will have 1x additional visit in clinic at baseline, followed by 5 additional visits via telephone at week 4, 6, 8, 12 and 24.

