## **11 STATISTICS AND DATA ANALYSIS**

### **11.1 Sample size calculation**

If Alpha-Stim AID CES has a comparable effect to IAPT high intensity psychological therapy interventions in patients with a primary working diagnosis of GAD, it will achieve an effect size of 1.04 (95% CI 0.88 to 1.23) in an intention to treat sample of 4,183 participants with pre-treatment GAD-7 score of 14.06 (s.d. 5.11) and post treatment GAD-7 score of 8.10 (s.d. 6.37) (Richards and Borglin, 2011). Reliable improvement was obtained after IAPT treatment for generalised anxiety disorder in 54.7%, reliable improvement plus clinically significant change in 40.1% and recovery in 46.0%.

However, to make a meaningful economic impact on NHS care, then Alpha-Stim AID CES does not need to be as effective as IAPT high intensity psychological therapy interventions. In a previous randomised controlled trial (Barclay and Barclay 2014), Alpha Stim CES reduced the mean Hamilton Anxiety score from 29.5 to 13.4 while sham Alpha Stim CES reduced it from 27.6 to 20.0 over 5 weeks  $p=0.001$ ,  $d=0.94$ , with 83% patients showing a drop of 50% in HAM-A score.

A meta-analysis of 14 Alpha Stim CES randomised controlled trials estimates an average effect size of 0.60. On this basis reliable improvement may be seen in 33%, reliable improvement plus clinically significant change in 24% and recovery in 28% cases.

The cost of IAPT high intensity psychological therapy intervention is estimated to be £2,895.00 per participant and £2,914.00 if stepped care was involved (Radhakrishnan et al, 2013). On a cost offset basis if Alpha-Stim AID CES cost £465.00, then reliable improvement plus clinically significant change (which would not necessitate high intensity treatment) in only 20% would be clinically and cost effective.

Taking all data into account, 60 patients would be required to complete Alpha Stim AID CES treatment and all assessments. However, to allow for drop-out from assessments, drop-out from Alpha-Stim AID CES, and choice in relation to IAPT high intensity psychological therapy intervention ,120 patients will be recruited.

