#### Any primary and community care contacts over the last 3 months

Indicate yes or no, by marking with a cross (X) in the relevant box.

	Yes	No
Participant has used any primary and community care services in the last 3 months		

If yes, provide further detail below.

	Service	Total number of contacts in last 3 months	Average duration of each attendance (minutes)
1	GP surgery		
2	GP home visit		
3	Practice nurse		
4	Community psychiatric nurse		
5	Walk-in centre		
6	Out-of-hours care		
7	Occupational therapist		
8	Social worker		

9	Advocate (eg, creative support)		
10	Home-help / home care worker		
11	Community support worker		
12	Psychiatrist		
13	Psychologist		
14	Other, please specify:		

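### The 12-week cost change from baseline to week 24 cannot estimate the cost offset the plan argues for, and its sign can differ from that offset

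*Combined protocol and SAP*

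**What the plan says.** - **Outcome.** Section 3.5 gives the CSRI outcome as "the change in cost impact for previous 12 weeks from baseline to week 24". Section 3.2 uses the same window: "over the previous 12 weeks, from baseline to week 24". The Study Summary is worded differently: "The endpoint will be the cost impact from baseline to week 24", with no 12-week window.
- **Instrument.** The CSRI in Appendix B looks back three months, for example "Any primary and community care contacts over the last 3 months". Sections 7.5 and 7.6 schedule it at day 1, week 12 and week 24. The Study Flow Chart puts the middle CSRI at week 6 instead.
- **Design.** Section 4 describes a "single-centre, naturalistic post-market clinical study of one CE marked device". Participants are on the step three waiting list during the first six weeks. Step three then proceeds as standard care, and "the current minimum waiting time for access to such therapy interventions is at least 6 - 8 weeks", counted from the initial approach. Device use ends by week 12 at the latest.
- **Economic argument.** Section 11.1 prices step three at £2,895 per participant (£2,914 with stepped care) and the device at £465. The saving comes from participants with "reliable improvement plus clinically significant change (which would not necessitate high intensity treatment"). The plan calls 20% of these enough and predicts 24% (29 of 120).
- **Analysis.** Section 11.3 plans means and standard deviations by visit. It names no comparator cost.

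**The concern.** Section 11.1 contrasts the same pathway with and without the device: therapy that does not happen, less what the device costs. Section 3.5 contrasts two periods in the same people, all of whom receive the device. These are different quantities.

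The two periods also differ for reasons other than the device. At entry participants are still waiting for step three, so the baseline window should hold essentially none of its cost. The week 24 window may hold some, all or none of it. Section 1 itself calls steps one and two relatively cheap and step three relatively expensive.

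Weeks 0 to 12 belong to neither window. The device period and any step three contact from about week 6 to week 12 therefore never enter the comparison. The device itself is on loan and has no line on the CSRI form.

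Section 2 says the study is designed chiefly to supply evidence to NICE and NHS England, including on economic impact. A cost figure whose sign depends on when therapy happens to start does not serve that purpose.

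**Working it through.** **Inputs**
- H, cost of step three: £2,895 (section 11.1).
- D, device cost: £465 (section 11.1).
- p, share avoiding step three: 20%, 24% or 50% (section 11.1; the 50% is the 60 of 120 expected to need no or minimal psychological treatment).
- u, step three uptake without the device: not given; section 11.1 implies 100%.
- f, share of step three cost falling in weeks 12-24: not given; anywhere from 0 to 1.
- B, baseline-window cost minus the non-step-three cost in weeks 12-24: not given; £500 and £1,500 are used below only as illustrations.

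**1. The plan's own figures.** 120 x 0.24 = 28.8, which rounds to 29. Break-even avoidance is 465 / 2,895 = 16.1%. At 20%, 465 - 0.20 x 2,895 = 465 - 579 = -£114, so 20% is sufficient, as stated, under full uptake.

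**2. The offset in section 11.1, D - pH.**
- p = 24%: 465 - 694.80 = -£229.80, about -£230. With £2,914: 465 - 699.36 = -£234.36.
- p = 50%: 465 - 1,447.50 = -£982.50.

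**3. Dependence on uptake, D - upH** (assuming avoidance applies among those who would take therapy up). At p = 24%:
- u = 60%: 465 - 0.60 x 694.80 = 465 - 416.88 = +£48.
- Break-even: u = 465 / 694.80 = 66.9%.

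**4. What section 3.5 measures.** Change = f x u(1 - p)H - B. There is no D in it, and no cost without the device. At p = 24%:
- u = 100%: remaining step three cost is 0.76 x 2,895 = £2,200 per participant.
- u = 60%: 0.60 x 0.76 x 2,895 = £1,320.

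| u | Offset (step 2 or 3) | f | B (assumed) | Change under 3.5 |
|---|---|---|---|---|
| 100% | -£230 | 0 | £500 | -£500 |
| 100% | -£230 | 0.25 | £500 | +£50 |
| 100% | -£230 | 0.5 | £500 | +£600 |
| 100% | -£230 | 0.5 | £1,500 | -£400 |
| 100% | -£230 | 1 | £500 | +£1,700 |
| 60% | +£48 | 0.25 | £500 | -£170 |

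The second, third and fifth rows show a rise although the device saves money. The last row shows a fall although it does not. With u = 100% and B = £500, the change turns positive once f exceeds 500 / 2,200 = 23%. At p = 50% the threshold is 500 / 1,447.50 = 35%, while the offset is a saving of £982.50.

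**The case against.** **The direction is not established.** The minimum wait runs from the initial approach, not from day 1. The minimum step three package is an assessment and two CBT sessions, which could be over before week 12. A long wait could push therapy past week 24. So f may be near 0. B is unknown too: section 6.1 sets no time limit on earlier step two care, and section 7.1 allows recruitment of people already on the waiting list. All of this stands. A reader might infer that the outcome will show a rise, that it mainly reflects position in the pathway, or that the distortion is £550 to £2,200 (25% to 100% of £2,200). The documents support none of these.

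**Cost effectiveness does not rest on this measure alone.** EQ-5D-5L and WASA also serve the secondary objective, and GAD-7 results bear on the 20% criterion. That is fair. But none of them measures cost, and a GAD-7 response does not show that a therapy course was avoided.

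**The Study Summary can be read as cumulative cost, and a week 12 CSRI is collected.** Both are true, and they make the repair cheap. The wording still conflicts with section 3.5, and neither version supplies a comparator.

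**A single-arm study has no counterfactual.** True, so any incremental cost has to be modelled. Section 11.1 already does this implicitly, with full uptake.

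**The before-after figure may never be offered as the device's economic impact.** The documents do not say which figure would be submitted. Section 2 says only that an assessment of economic impact is needed.

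The CSRI form also has no named line for IAPT therapy, only entries such as psychologist and other. That is a separate matter: complete recording would not create a comparator.

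**Conclusion.** The concern holds as a mismatch between the outcome and the argument. The cost change in sections 3.2 and 3.5 omits weeks 0 to 12 and has no comparison without the device. It cannot estimate the offset in section 11.1, and its sign can differ from that offset in either direction. Which way it goes depends on f and B, and the documents give neither.

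The -£230 per participant at 24% avoidance is conditional on everyone otherwise having step three. If avoidance applies only among those who would take it up, the saving is gone below about 67% uptake and becomes a cost of about £48 at 60%. It should not be read as an established saving that the outcome merely fails to detect.

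The sponsor should make this change before any economic result is produced. The data needed for a cumulative cost are already planned.

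**What to change.** 1. **Outcome wording.** In sections 3.2 and 3.5 and the Study Summary, define the cost outcome as mean total cost per participant from day 1 to week 24. Take it from the week 12 and week 24 CSRI, whose three-month recall covers roughly the whole period. Add the device cost explicitly and state the price used: section 11.1 has £465, and section 8.2 gives £499 for private purchase.
2. **Schedule.** Reconcile the Study Flow Chart (middle CSRI at week 6) with sections 7.5 and 7.6 (week 12). With forms at weeks 6 and 24 only, most of weeks 6 to 12 would be uncovered, which is when step three may begin.
3. **Economic impact.** Report it separately as a modelled contrast of like with like: device cost plus observed step three cost in the study, against step three uptake without the device x £2,895 (or £2,914). Show uptake over a range such as 60% to 100%. State that therapy after week 24 is not captured, which flatters the device when set against a per-participant cost with no stated time limit.
4. **What to avoid.** Do not set total CSRI cost, which includes hospital, GP, travel and informal care, against step three cost alone. That would charge all other care to the device.
5. **Baseline.** Keep baseline CSRI cost as description. Do not present the change from baseline as the device's cost effectiveness.

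The cost is revised wording in three places and a small scenario table, with no new visit. The downside is that the comparator is modelled, so the economic claim becomes more modest.

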### 3.6 Tertiary outcome measures

The tertiary objectives will be measured using the PHQ-9, which is a participant-reported measure of depressive symptomatology. Additionally, the objective will be measured using the Athens Insomnia Scale, which is participant-reported measure of sleep difficulty.

- The outcome measure for **reliable improvement of depressive symptomology** is defined as participants who reach a score reduction of 6 or more from baseline to week 24.
- The outcome measure for **clinically significant improvement of depressive symptomology** is defined as participants with a score of 10 or more at baseline, who reach 9 or fewer by week 24.
- The outcome measure for **recovery of depressive symptomology** is defined as participants with a score of 11 or more at baseline, who reach 8 or fewer by week 24.
- The outcome measure for **reliable improvement of insomnia** has no current, standardised definition, and so in this study, will be defined as participants who reach a score reduction of 50% or more from baseline to week 24.
- The outcome measure for **clinically significant improvement of insomnia** is defined as participants with a score of 6 or more at baseline, who reach 5 or fewer by week 24
- The outcome measure for **recovery of insomnia** is defined as participants with a score of 6 or more at baseline, who reach 4 or fewer by week 24.

## 4 STUDY DESIGN

This is a single-centre, naturalistic post-market clinical study of one CE marked device within intended purpose over 24-week follow-up period. The study will enrol patients with a primary working diagnosis of moderate-to-severe GAD who did not improve (continued to have a primary working diagnosis of moderate-to-severe GAD) with previous low intensity psychological therapy intervention.

Participants indicated for high intensity psychological therapy intervention will be approached by their routine care provider (either a Psychological Wellbeing Practitioner (PWP) or Cognitive Behavioural Therapist) with information about this study when they are contacted to discuss a step-up to step 3 high intensity therapy. From this initial approach, the current minimum waiting time for access to such therapy interventions is at least 6 - 8 weeks.

Participants who consent to enrolment will undertake 60 minute self-directed Alpha-Stim AID CES treatment sessions in their own homes on a daily basis for 6 weeks. During this 6-week period, participants will be on the waiting list for high intensity psychological therapy intervention.

Following 6 weeks of Alpha-Stim AID device treatment, participants have the option to receive a further 6 weeks of treatment, which may coincide with start of high intensity psychological therapy interventions as clinically indicated. This option is available to make the study design more comparable to real-world scenarios.

Participants wishing to discontinue use of the Alpha-Stim AID device will return the device and any unused electrode pads to the research nurse via pre postage paid envelope.

Following a maximum of 12 weeks' treatment with Alpha-Stim AID device, all participants will cease to receive treatment on study. At this time-point, all participants will return the device and any unused electrode pads to the research nurse via pre postage paid envelope.

Participants will have 1x additional visit in clinic at baseline, followed by 5 additional visits via telephone at week 4, 6, 8, 12 and 24.

All participants will continue to receive standard care assessment, as undertaken by the NHS IAPT service, standard care high intensity psychological therapy intervention as clinically indicated and provided by the NHS IAPT service, and standard care pharmacological treatment as prescribed by the participant's GP. Participation in this study will not influence nor compromise standard care treatment – all study procedures are additional to standard care. Participation in the study will have no impact upon the duration of the waiting time for high intensity psychological therapy intervention.

## **5 STUDY SETTING**

Participants will be enrolled from the clinical caseload of the three teams comprising Leicestershire and Rutland Improving Access to Psychological Therapies (IAPT) service (part of Nottinghamshire Healthcare NHS Foundation Trust). These participants will have 1x additional baseline visit in clinic (which will be the routine facilities of the IAPT service, comprising a GP clinic room or community venue) in addition to 5x additional visits via telephone at week 4, 6, 8, 12 and 24.

Participants will continue to receive standard of care assessments and interventions as routine, which will take place in routine facilities.

Study delivery will be undertaken by staff within the IAPT service, in addition to staff from NIHR CRN East Midlands.

## **6 ELIGIBILITY CRITERIA**

### **6.1 Inclusion criteria**

- Primary working diagnosis of moderate-to-severe GAD indicated via a GAD-7 score of 10 or more at baseline visit
- Previous treatment within an IAPT service with step two low intensity psychological therapy intervention
- Indicated for step three high intensity psychological therapy intervention and on the waiting list OR deemed unsuitable for step two within an IAPT service
- Capable of giving informed consent
- Female participants of child-bearing potential must have a negative urine human chorionic gonadotropin dipstick pregnancy test
- Female participants of child-bearing potential must be practising a highly effective method of contraception (failure rate of less than 1% per year when used consistently and correctly and agree to remain on a highly effective method throughout the 6 or 12 week treatment period. Examples of highly effective contraceptives include: barrier condoms, intrauterine device (IUD), intrauterine hormone-

releasing system (IUS), vasectomised partner, sexual abstinence (refraining from heterosexual intercourse), and oestrogen and progestogen containing hormonal contraception associated with ovulation.

- 18 years of age or above at baseline visit
- Able to understand written and verbal English

## **6.2 Exclusion criteria**

- Primary working diagnosis of a mental disorder other than moderate-to-severe GAD (but other mental and anxiety disorders as secondary comorbidities is not an exclusion criteria)
- No previous treatment within an IAPT service with step two low intensity psychological therapy intervention
- Not indicated for step three high intensity psychological therapy intervention and not on the waiting list
- Requiring urgent clinical care
- Female participants of child-bearing potential with a positive urine human chorionic gonadotropin dipstick pregnancy test
- Female participants of child-bearing potential not willing to practice a highly effective method of contraception during the treatment period
- Implantation with a pace maker
- Implantation with an implantable cardioverter defibrillator (ICD)
- Incapable of giving informed consent
- 17 years of age or less at baseline visit
- Unable to understand written and verbal English

